1.0 Study Summary

Study Title	Eating Disorder Individualized Therapeutics-Naltrexone Neuroimaging
Study Design	Open label, prospective trial
Primary Objective	Modulation of reward system measured by fMRI
Research Intervention(s)/ Investigational Agent(s)	Naltrexone 50 mg oral tablet x 1
Study Population	Adolescents aged 13-21 years
Sample Size	Pre-screening up to 1000 individuals, Up to n=50
Study Duration for Individual Participants	1 study visit (~10 hours)
Study Specific Abbreviations/ Definitions	FMRI – functional magnetic brain imaging BOLD – blood oxygenation level dependent AN – anorexia nervosa BN – bulimia nervosa BED – binge eating disorder ED – eating disorder ROI – region of interest MID – monetary incentive delay PFV – passive food view EPSI – eating pathology symptom inventory AKR – aldoketoreductase OPRM – opioid receptor mu NTX - naltrexone

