2.0 Objectives

The overall goal of this project is to generate pilot data to support the development of fMRI as a pharmacodynamic biomarker of opioid antagonism in adolescents with ED, which will be accomplished through the following specific aims (SA):

SA1. Define the extent of within individual reward system modulation and identify the brain region most responsive to opioid antagonism in adolescents with binge/purge ED. We will use fMRI to detect percent blood oxygenation level dependent (%BOLD) changes pre- and post-opioid antagonist treatment (i.e., naltrexone) within individuals during a food reward and general reward-related task using regions of interest (ROI) analysis. We hypothesize that the anterior cingulate cortex (ACC) will be most responsive to naltrexone in adolescents with ED during food reward.

SA2. Determine the fMRI reward paradigm most sensitive to opioid antagonism in adolescents with binge/purge ED. Using the method described in SA1, we anticipate that the food paradigm will be more sensitive (e.g., higher t-score) in reward ROI to opioid antagonism in our target population.

SA3. Describe the naltrexone exposure-brain response relationship using fMRI in adolescents with binge/purge ED. We will link pharmacokinetic (PK) parameters of exposure with %BOLD change in subjects during the reward paradigms using ROI analysis. Based on our preliminary data suggesting

SHORT TITLE: Naltrexone Neuroimaging

widely variable maximum plasma concentrations (C_{max}) of naltrexone in adolescents with ED (17-fold), we hypothesize that reduced C_{max} will be associated with reduced activation in reward-related ROIs.

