4.0 Study Endpoints

Outcomes	Exploratory Outcomes

Primary:
 
• RESPONSE (SA1) - defined by $\Delta\%BOLD$ pre/post-ntx in ROI 
Secondary:
 
▪ ROI (SA1) - defined by coordinates with largest response▪ OPTIMAL PARADIGM (SA2) – paradigm (PFV or MID) resulting in larger response▪ EXPOSURE (SA3) – defined by ntx C_{max}	
▪ RESPONSE x OPRM1 genetic variation▪ RESPONSE x metabolomic profile▪ RESPONSE x impulsivity▪ RESPONSE x negative urgency▪ RESPONSE x delayed discounting▪ EXPOSURE x AKR1C4 genetic variation▪ EXPOSURE x metabolomic profile

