6.0 Inclusion and Exclusion Criteria

Inclusion Criteria

- Adolescents aged 13-21 years
- *Eating disorder diagnosis per DSM-V criteria that is characterized by binge eating (defined as loss of control of eating resulting in large amount of food consumed in a short period of time) and/or purging (e.g., vomiting, excessive exercising, laxative use)*
- *Stable medication regimen (no dose or drug changes in the past 4 weeks)*
- *Participant and parent/legal guardian (if under 18 years) are willing and able to provide informed permission/assent/consent for the study*

Exclusion Criteria

- *Pregnant (via UCG)*
- *Prior hypersensitivity reaction to naltrexone (e.g., anaphylaxis)*
- *Non-removable metal in the body*
- *Current naltrexone use*
- *Self-reported opioid use in the past 7 days*
- *A language barrier (e.g., non-English speaking) for the participant that precludes communication and/or ability to complete all study-related requirements.*

English speaking participants whose parent/guardian are non-English speaking may be consented using a translated PAC form. Participants will have suitable English proficiency to complete study questionnaires and logs. Determination of proficiency will be at the discretion of the PI. Non-English speaking participants are excluded because the validated questionnaires used in this study to measure eating disorder symptomatology (EPSI) is not yet available in languages other than English. This assessment was chosen because of the ability to discriminate eating disorder behaviors and validation in the target age range. It is also the main assessment used in the CM Eating Disorder Center and thus parallels clinical practice.

Non-English Speaking Subjects:

- Parent/guardians only
- language(s) other than English understood by prospective parent/guardians: Spanish
- ORI Translation Program to translate the PAC form

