9.0 Study Procedures

The study will involve a screening encounter and one study day.

Study Visit Element	Main Procedures/Data Collected	Approximate Clock Time
Screening and Consent	Inclusion/exclusion criteria, Consent	In person, telephone or e-consent prior to study visit
I/E confirmation and medical History	Inclusion/exclusion criteria review and confirmation, medical history, anthropometrics, pregnancy test (if applicable)	7 am
Meal #1 (1 hour before scan #1)	Standardized CHO:PRO:FAT content	8 am
Baseline/pre-dose measures	Impulsiveness (BIS-brief), negative urgency (UPPS-P subscale); delayed discounting, blood draw (targeted metabolomic panel, genetic analysis)	8:20 am
fMRI scan #1	Hunger rating, reward related tasks (PFV, MID)	9 am
Naltrexone (NTX) dosing	Naltrexone 50 mg PO 2 hours prior to scan #2	10:30 am
Meal #2 (1 hour before scan #2)	Standardized CHO:PRO:FAT content	11:30 pm

SHORT TITLE: Naltrexone Neuroimaging

fMRI scan #2 (2 hours post-NTX)	Hunger rating, reward related tasks (PFV, MID)	12:30 pm
Pharmacokinetic analysis	3 mL blood samples - pre-dose, 0.5, 1, 1.5, 2, 3, 4, 6, 7 hours post-naltrexone dose.	5:30 pm (last PK draw & study end)

Screening and consent. The study will be reviewed in depth with the participant and his/her parents/legal guardian when applicable. They will be provided sufficient time to review the PAC form, have all questions answered, and concerns addressed. If they agree to participate, they will sign the PAC form. This may occur in person, over the phone (using telephone script) or via e-consent. In the event the parent/guardian is non-English speaking, interpreter will be offered along with provision of translated PAC form. The participant must have English proficiency to complete study procedures (see inclusion criteria).

Screening failures (i.e., participants meeting any exclusion criteria) may be screened again at a future time point at the discretion of the Principal Investigator.

Pre-visit Planning. Scheduled participants may be contacted ahead of study with a reminder of their study appointment. Once PAC has been obtained, participants will be reminded to avoid food for 4 hours prior to study day.

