Opioid Antagonism. A single oral dose of naltrexone hydrochloride 50 mg tablet will be administered by licensed study staff 2 hr (± 1 hr) before scan #2. Complete opioid receptor blockade is evident at 1-hour post-dose, which overlaps with time at maximum concentration in plasma (T_{max}) and persists for at least 24 hours post-dose in adults(13, 14). In our PK study in adolescents with ED, preliminary analysis shows T_{max} at 2 hour. Thus, optimal timing of 2 hours was conservatively chosen while providing a feasibility window supported by evidence. Naltrexone is well-tolerated and difficult to distinguish from placebo in blinded trials(15-17). CM IDS pharmacy will dispense study medication. Naltrexone hydrochloride 50 mg tablet is FDA approved for opioid and alcohol use disorder and used off-label for the treatment of compulsive and impulsive behaviors in children, adolescents and adults. Examples of compulsive and impulsive pertinent to this study include binge eating and purging (e.g., vomiting). Evidence for safe and efficacious use of naltrexone for these behaviors is available (4). This study does not significantly increase the risk associated with naltrexone as the commercially available dose, formulation and route chosen is consistent with current clinical practice at doses ranging from 50 -200 mg/day. Additionally, a meta-analysis revealed that naltrexone,

SHORT TITLE: Naltrexone Neuroimaging

when compared with placebo, is not associated with serious adverse events(17). It is not the intent of this study to generate data for submission to the FDA or to support a significant change in advertising of the drug. Storage, control and dispensation of the drug will occur through collaboration with IDS pharmacy. Use of naltrexone for this study meets criteria for IND exemption, category #1 (21 CFR 312.2(b)(1)).

Meals. Imaging will occur in the fed state using a standardized meal to avoid prolonged fasting that may compromise the health and recovery of the target population. This is not expected to meaningfully interfere with the detection of reward system modulation within individuals. Previous fMRI studies in adults suggest that individuals with disordered eating and/or obesity/overweight may exhibit stronger reward activation in the fed state compared with healthy controls(18, 19). Healthy weight individuals still exhibit strong reward activation, particularly in the ACC, in the fed versus fasted state, even though small reductions are seen(20).

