21.0 Withdrawal of Subjects

Participants may withdrawal at any time during the study. To withdrawal participants will notify the study team in writing that they wish to withdrawal. Study procedures will cease. Any data collected will be retained for potential analysis.

22.0 Data Analysis:

Outcome analyses. Outcomes are defined per Table 2. SA1. *Response*. fMRI data will be analyzed in AFNI in two ways: 1) region of interest (ROI) analysis in *a priori* reward ROIs including the ventromedial prefrontal cortex, ACC and striatum and 2) exploratory whole brain analysis to identify regions outside the reward network that may also respond to naltrexone (e.g., insula, dorsolateral prefrontal cortex, dorsal ACC). We have chosen to use a pre-defined ROI analysis which will be selected from a meta-analysis of passive viewing food tasks and MID studies using neurosynth.org or similar(29). Although ROI approaches do present challenges in fMRI analyses, this hypothesis-driven approach has been chosen to focus the primary analysis to test targeted reward related changes associated with treatment. Exploratory analysis described below will use advanced fMRI analysis approaches to take advantage of the richness of the whole-brain data. SA2. *Optimal paradigm*. The %BOLD changes will be compared between paradigms by LMM using paradigm (PFV, MID) and time (pre, post) as fixed-effects, and random individual and/or paradigm intercepts. SA3. The changes in %BOLD and changes in *Exposure* (log-scale) will be correlated by Pearson's correlation coefficient; the 95% CI will be estimated by non-parametric bootstrap using the bias-corrected and accelerated method.

PKPD analysis. Kinetica 5.0 or similar software will be used to model PK parameters (e.g., C_{max} , AUC_{0-inf}).

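### Is the SA3 correlation undefined because Section 22.0 speaks of a change in Exposure when each participant has only one Cmax?

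*Combined protocol and SAP*

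**What the plan says.** The SA3 sentence in Section 22.0 pairs changes in %BOLD with Exposure: "changes in *Exposure* (log-scale) will be correlated by Pearson's correlation coefficient". The 95% interval is to come from a bias-corrected and accelerated bootstrap. The same section states at its start that outcomes are defined in a table, and it sets *Exposure* in italics as a defined term.

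The outcomes table in Section 4.0 gives Exposure as "defined by ntx C_{max}". In that table only Response carries a pre/post difference.

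Section 2.0 says that SA3 will "link pharmacokinetic (PK) parameters of exposure with %BOLD change in subjects", and its hypothesis reads "we hypothesize that reduced C_{max} will be associated with reduced activation in reward-related ROIs".

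The design gives each person one exposure profile. Section 1.0 lists "Naltrexone 50 mg oral tablet x 1", and Section 9.0 lists "3 mL blood samples - pre-dose, 0.5, 1, 1.5, 2, 3, 4, 6, 7 hours post-naltrexone dose". Section 6.0 excludes "Current naltrexone use" and requires a medication regimen unchanged for 4 weeks.

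**The concern.** A correlation needs two variables that can be computed for every participant. %BOLD is measured before and after naltrexone, so its change exists. Cmax is the peak of a single post-dose profile, so it has no pre-dose counterpart and its change is not defined anywhere.

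The one available comparator is the pre-dose blood sample. If that is zero, a difference in logs requires log(0), and no rule for values below quantification is given.

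SA3 is one of three specific aims, and Exposure is a listed secondary outcome. If analysts had to invent the exposure variable after seeing the data, they would have alternatives to choose from: Section 22.0 also mentions AUC, and Section 9.0 measures the active metabolite 6-beta-naltrexol. A free choice among these would weaken the one planned exposure-response result.

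**Working it through.** The plan states no expected correlation, power or alpha for SA3, so there is no figure to reproduce. The check is whether the possible readings of the sentence give different answers.

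**Inputs.** One dose and one visit (Section 1.0); one pre-dose and eight post-dose samples (Section 9.0); Exposure = naltrexone Cmax (Section 4.0); up to 50 participants (Section 5.0).

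**Pre-dose level.** Current users are excluded, and anyone who stopped naltrexone within 4 weeks would have had a drug change and fail the stable-regimen criterion. A pre-dose concentration of zero or below quantification is therefore expected. This is an inference; no pre-dose levels are reported.

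**Readings.** Let C be a participant's Cmax and Y the change in %BOLD.

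1. Level: X = log(C).
2. Log of the rise from pre-dose: X = log(C - 0) = log(C), the same variable.
3. Log difference with a common value k substituted for unquantifiable pre-dose results: X = log(C) - log(k). Pearson's r is unchanged when a constant is subtracted, so r(X, Y) = r(log C, Y). This holds in every bootstrap and jackknife sample too, so the interval is the same for the same resamples.
4. Log difference from an exact zero: X = log(C) - log(0), infinite for every participant.

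**Numerical check, n = 50, illustrative data.**

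| Exposure variable | r |
|---|---|
| log(C) | -0.361 |
| log(C - 0) | -0.361 |
| log(C) - log(0.01) | -0.361 |
| log(C) - log(0.1) | -0.361 |
| log(C) - log(0.5) | -0.361 |
| log(C) - log(0) | not computable |

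Over 12,000 simulated trials of 50 with a true r of 0.40 (4,000 at each log-SD of Cmax: 0.66, 0.70 and 0.92), readings 1 to 3 differed by less than 1e-15.

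**A less natural workaround.** An analyst could use log(1 + concentration), although nothing in the documents suggests it. With median Cmax assumed at 1 or 5 units, it lowered r by at most 0.013 on average and moved it by no more than 0.02 to 0.07 in 95% of trials, depending on the units. For scale, the approximate standard error of r at n = 50 and r = 0.40 is (1 - 0.40²)/√(50 - 3) = 0.84/6.86 = 0.12. The average shift is about a tenth of that (0.013/0.12 = 0.11).

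**The case for a change.** The strongest case for acting is that the text is wrong as it stands and the edit costs one phrase. An analysis section should name its variable, and a reader should not have to assemble it from Sections 2.0 and 4.0.

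The mismatch does stand. The freedom it is said to create does not. The definition that Section 22.0 relies on names the analyte and the parameter, which excludes AUC and the metabolite. The outcomes table carries no number in the text as read, but it is the only one in the document. Nor would replacing the phrase with log(Cmax) be a clean repair: changes in %BOLD and log(Cmax) could still be read as changes in both, and the analyte would be left out.

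A second argument is that Cmax may not reflect exposure at the scan. The dose "will be administered by licensed study staff 2 hr (± 1 hr) before scan #2", so scan #2 may begin 1 to 3 hours after dosing, while Cmax is taken over samples to 7 hours and may fall after the scan. That questions the choice of exposure measure, not whether the variable is defined. Under an assumed one-compartment model with smooth absorption, log Cmax and log mid-scan concentration correlate 0.975 to 0.999 for starts at 1 or 2 hours, and 0.919 to 0.997 for a start at 3 hours. With measures correlated 0.92 to 0.99 and a true r of 0.40 with one of them, the two coefficients differ by 0.004 to 0.032 on average at n = 50, and the difference points the wrong way in 27 to 42% of trials. A second analysis would seldom tell the two apart. It could matter if a subgroup absorbed the drug late, which the documents do not establish.

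**Conclusion.** This is a clerical slip with no effect on the result. The word *changes* belongs to %BOLD and was carried over to Exposure. Sections 2.0 and 4.0 both identify the intended variable as the logarithm of naltrexone Cmax. The computable readings of the sentence give the same coefficient and the same interval. The remaining reading, a log difference from exact zero, returns no number and so cannot mislead anyone.

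The conclusion rests on pre-dose concentrations being zero or below quantification. Measurable pre-dose levels that differed between participants could separate the readings, but nothing in the documents points to them and the eligibility criteria make them unlikely. No sample size or power statement depends on this point, and the study is presented as a source of pilot data. No change to the plan is called for.

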23.0 Adverse Events and Unanticipated Problems

Any adverse event that occurs during study participation will be recorded. The primary safety end point will be based on frequency of AEs during the Study Day.

Definition and Grading Intensity of Adverse Events

An adverse event is defined as any undesired change in the body structure (signs) or body function (symptoms), whether or not considered drug-related. For the purposes of this study, drug-related is independent from study-related, as described above. During the entire duration of the study, subjects will be instructed to report all adverse events. All adverse events, whether volunteered, elicited, or noted on physical examination, will be recorded throughout the study. Each adverse event will be described by 1) its duration 2) severity grade (see below for definition), 3) its relationship to the medication studied (none, possible, probable, definite) 4) the action(s) taken.

The severity of adverse events will be categorized as follows:

SHORT TITLE: Naltrexone Neuroimaging

- MILD = Experience is minor and does not cause significant discomfort to subject or change in activities of daily living (ADL); subject is aware of symptoms but symptoms are easily tolerated.
- MODERATE = Experience is an inconvenience or concern to the subject and causes interference with ADL but the subject is able to continue with ADL.
- SEVERE = Experience significantly interferes with ADL and the subject is incapacitated and/or unable to continue with ADL.

Serious Adverse Event (SAE) Reporting

A serious adverse drug experience (by FDA definition) is any adverse test material event occurring at any dose that results in any of the following outcomes:

- Death
- Life-threatening adverse experience
- Inpatient hospitalization or prolongation of existing hospitalization
- Persistent or significant disability/incapacity
- Congenital anomaly/birth defect

Any serious adverse event will be reported verbally to the primary investigator (see contact info below) and naltrexone prescriber within 24 hours of notification. Written notification will be sent to the IRB within 3 working days.

[name], APRN [REDACTED], [contact]

NOTE: The term “severe” is often used to describe the intensity (severity) of a specific event (as in mild, moderate, or severe myocardial infarction); the event itself, however, may be of relatively minor medical significance (such as a severe headache). This is not the same as “serious,” which is based on participant/event outcome or action criteria usually associated with events that pose a threat to the participant’s life or functioning. Seriousness (not intensity) serves as a guide for defining regulatory reporting obligations.

24.0 Provisions to Monitor the Data to Ensure the Safety of Subjects

A data safety/monitoring committee will be established to monitor the safety of the study and include the PI, senior mentor(s), and a medical provider not part of the study. Cumulative and new safety data will be reviewed at least every 6 months or sooner if serious adverse event occurs.

Data reviewed will include any adverse event occurring during the study day or reported by participant to have occurred after the study, but thought to be associated with the study (via participant initiated communication).

25.0 Data Management

Data will be collected and recorded during the study by members of the study team. Categories of data collected as listed in section 9.0 The investigator and members of the research team are bound to keep this information confidential and will do everything within their power to avoid loss of confidentiality. The documents will be stored on the hospital’s secure system (e.g., OneDrive) with access restricted to members of the study team.

The investigator agrees to adhere to the document retention procedures and retain essential documents for 3 years after the completion or discontinuation of the trial. Essential documents include:

1. IRB approvals for the study protocol and all amendments
2. DCF
3. subjects' signed PAC forms
4. any other pertinent study documents

26.0 Multi-site Research

Study procedures and imaging data analysis will occur at Hoglund Biomedical Imaging Center, part of the CTSA located on the campus of University of Kansas Medical Center. Additional sample processing and data analysis will occur at Children's Mercy Kansas City.

CM will be the IRB of record with a request for KUMC to rely on CM.

27.0 Equitable Selection and Vulnerable Populations

Age range was chosen based on relevance to the population of interest (e.g., adolescents with eating disorders) and alignment with validated eating disorder symptom burden questionnaire (EPSI).

Vulnerable Populations:

 Children/Minors (under 7 years of age)	 Pregnant Women
 Children/Minors (7-17 years of age)	 Adults with impaired decision-making capacity
 Neonates (infants less than 30 days old)	 CM Employees
 Neonates of Uncertain Viability (infants less than 30 days old)	 CM Students/Residents/ Fellows (categorized as "trainees")
 Non-Viable Neonates (infants less than 30 days old)	 Economically or Educationally Disadvantaged Persons
 Wards of the State	 Prisoners
 Fetuses	

For CM employees or trainees, the risk of coercion will be minimized by ensuring that they will not be recruited or enrolled by their direct supervisor and through reassurance that their decision regarding participation does not impact their employment or educational status at CM.

REFERENCES

